##### 6.11.1 BMS Recommended Endocrine Adverse Event Management Algorithm

These suggested management guidelines are taken from the BMS algorithms provided in the Investigator’s Brochure.

Consider visual field testing, endocrinology consultation, and imaging.

Toxicity (CTCAE v.5)	Management	Follow-up
Asymptomatic TSH elevation	
 
Continue protocol therapy
 
If TSH < 0.5 x LLN, or TSH > 2X ULN, or consistently out of range in 2 subsequent measurements: include fT4 at subsequent cycles as clinically indicated
 
Consider endocrinology consult
 
	
Symptomatic Endocrinopathy	
 
Evaluate endocrine function
 
Consider pituitary scan
 
 
Symptomatic with abnormal lab/pituitary scan:
 
 
Hold infusion
 
1-2 mg/kg/day methylprednisolone IV or oral equivalent
 
Initiate appropriate hormone therapy
 
 
No abnormal lab/pituitary MRI scan but symptoms persist:
 
 
Repeat labs in 1-3 weeks/ MRI in 1 month
 
	
If improves (with or without hormone replacement):
 
 
Taper steroids over at least 1 month
 
Consider prophylactic antibiotics for opportunistic infections
 
Patients with adrenal insufficiency may need to continue steroids with mineralocorticoid component
 

Suspicion of adrenal crisis (e.g. severe dehydration, hypotension, shock out of proportion to current illness)	
 
Discontinue protocol therapy
 
Rule out sepsis
 
Stress dose of IV steroids with mineralocorticoid activity
 
IV fluids
 
Consult endocrinologist
 
If adrenal crisis ruled out, then treat as above for symptomatic endocrinopathy
 
	

Patients on IV steroids may be switched to an equivalent dose of oral corticosteroids (e.g. prednisone) at start of tapering or earlier, once sustained clinical improvement is observed. Lower bioavailability of oral corticosteroids should be taken into account when switching to the equivalent dose of oral corticosteroids.

6.12 **Dose Modifications for Fever**

Fever	Management/Next Dose of Nivolumab ± Ipilimumab
≤ Grade 1	Continue protocol therapy
Grade 2	Hold until ≤ Grade 1. If resolves to ≤ Grade 1 within 7 days, resume at same dose level. If fever does not resolve to ≤ Grade 1 within 7 days, discontinue protocol therapy.
Grade 3	Hold until ≤ Grade 1. If resolves to ≤ Grade 1 within 24 hours, resume at same dose level. If fever does not resolve to ≤ Grade 1 within 24 hours, discontinue protocol therapy.

Fever	Management/Next Dose of Nivolumab ± Ipilimumab
Grade 4	Off protocol therapy
Patients with fever should be evaluated as clinically appropriate. Patients may experience isolated fever during infusion reactions or up to several days after infusion. Evaluation over the course of 1-2 weeks should be done for other autoimmune events that may present as fever	

**6.13 Dose Modifications for Renal Adverse Events**

Dose modifications for renal adverse events will be per [Section 6.2](#) if DLT definition is met. Refer to algorithm below for recommended management guidelines.

**6.13.1 BMS Recommended Renal Adverse Event Management Algorithm**

These suggested management guidelines are taken from the BMS algorithms provided in the Investigator’s Brochure.

Toxicity (CTCAE v.5)	Management	Follow-up
Grade 1 Creatinine Increased	
 
Continue protocol therapy
 
	
If worsens:
 
 
Treat as Grade 2/3 or 4
 

Grade 2 or 3 Creatinine Increased	
 
Hold infusion
 
Monitor creatinine every 2-3 days
 
0.5-1 mg/kg/day methylprednisolone or oral equivalent
 
Consider renal biopsy
 
	
If improves to Grade 1 or baseline:
 
 
Taper steroids over at least 1 month
 
Consider prophylactic antibiotics for opportunistic infections.
 
 
If elevations persists > 7 days or worsen:
 
 
Treat as Grade 4
 

Grade 4 Creatinine Increased	
 
Discontinue protocol therapy
 
Monitor creatinine weekly
 
1 to 2 mg/kg/day methylprednisolone IV or IV equivalent
 
Consult nephrologist
 
Consider renal biopsy
 
	
If improves to Grade 1:
 
 
Taper steroids over at least 1 month and add prophylactic antibiotics for opportunistic infections
 

Patients on IV steroids may be switched to an equivalent dose of oral corticosteroids (e.g. prednisone) at start of tapering or earlier, once sustained clinical improvement is observed. Lower bioavailability of oral corticosteroids should be taken into account when switching to the equivalent dose of oral corticosteroids.

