6.5.1 BMS Recommended Hepatic Adverse Event Management Algorithm

These suggested management guidelines are taken from the BMS algorithms provided in the Investigator’s Brochure.

Consider imaging for obstruction.

Toxicity (CTCAE v.5)	Management	Follow-up
Grade 1* AST or ALT, and/or bilirubin increased	
 
Continue protocol therapy
 
	
 
Continue routine LFT monitoring per Table 8.1
 
 If worsens: 
 
Treat as Grade 2 or 3/4
 

Toxicity (CTCAE v.5)	Management	Follow-up
Grade 2* AST or ALT, and/or bilirubin increased	
 
• Hold infusion
 
• Increase LFT monitoring to every 3 days
 
	
If improves to baseline:
 
 
• Continue routine LFT monitoring per Table 8.1
 
• Resume protocol therapy
 
 
If elevations persist >5-7 days or worsen:
 
 
• 0.5-1 mg/kg/day methylprednisolone IV or oral equivalent
 
• When LFT returns to grade 1 or baseline, taper steroids over at least 1 month
 
• Consider prophylactic antibiotics for opportunistic infections
 

Grade 3 or 4* AST or ALT, and/or bilirubin increased	
 
• Discontinue protocol therapy
 
• Increase LFT monitoring to every 1-2 days
 
• 1-2 mg/kg/day methylprednisolone IV or oral equivalent**
 
• Add prophylactic antibiotics for opportunistic infections
 
• Consult gastroenterologist
 
	
If improves to Grade 2:
 
 
• Taper steroids over at least 1 month
 
 
If does not improve in > 3-5 days, worsens or rebounds:
 
 
• Add mycophenolate mofetil 600 mg/m^2/dose (max 1 g/dose) BID
 
• If no response within an additional 3-5 days, consider other immunosuppressants per local guidelines
 

Patients on IV steroids may be switched to an equivalent dose of oral corticosteroids (e.g. prednisone) at start of tapering or earlier, once sustained clinical improvement is observed. Lower bioavailability of oral corticosteroids should be taken into account when switching to the equivalent dose of oral corticosteroids.

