 Women of childbearing potential require a negative pregnancy test prior to starting treatment. Men and women must be willing to adhere to effective contraception during the study and for 5 months after the last dose of nivolumab for women of childbearing potential and 7 months after the last dose of nivolumab for men sexually active with women of childbearing potential. Abstinence is an acceptable method of birth control.

 If patients have Grade 4 neutropenia then CBCs should be checked at least every other day until recovery to Grade 3 or until meeting the criteria for dose limiting toxicity.

- 3 If patients develop Grade 4 neutropenia then CBCs should be checked every 3 to 4 days until recovery to Grade 3
- 4 Free T4 should also be measured for patients with an abnormal TSH level. Guidance on the management of patients who develop hypothyroidism is included in [Section 7.3.4](#).
- 5 Tumor Disease Evaluation should be obtained on the next consecutive cycle after initial documentation of either a PR or CR. Please note that if the institutional investigator determines that the patient has progressed based on clinical or laboratory evidence, he/she may opt not to confirm this finding radiographically. If tumor growth is > 20% but < 40%, imaging to include target lesions must occur every cycle if clinically indicated, or if “pseudoprogression” appears based on inflammatory response, and the same radiographic and clinical criteria must be met in order to remain on study (See [Section 12.2.1](#)).
- 6 See [Section 8.3.2](#) and [Appendix III](#) for timing of PK studies.
- 7 Patients who are removed from therapy during Cycle 1 after receiving the dose of nivolumab on Day 15 should have their last PK sample collected on Day 28 of Cycle 1.
- 8 See [Section 8.4.2](#) and [Appendix IV](#) for timing of vaccine antibody and section [8.8.2](#) and [Appendix VII](#) for timing of cytokine studies.
- 9 See [Section 8.5.2](#) and [Appendix V](#) for timing of ADA studies.
- 10 See [Section 8.6](#) and [Appendix VI](#) for instructions for submitting tumor specimens. If tissue blocks or slides are unavailable, the study chair must be notified prior to study enrollment.
- 11 In the event a subject requires a biopsy for surgery and tumor tissue is removed, tissue will be requested for PD-L1 and CD8 Expression analysis (required, if available).

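### The suggested renal algorithm checks creatinine less often at Grade 4 (weekly) than at Grade 2 or 3 (every 2-3 days), while the hepatic and blood-count rules tighten as severity rises

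*Combined protocol and SAP*

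**What the plan says.** Section 6.13 handles dose modification for renal events through the general DLT rule of Section 6.2. For management it tells sites: "Refer to algorithm below for recommended management guidelines". The algorithm in Section 6.13.1 is described as suggested guidance taken from the Investigator's Brochure.

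- **Grade 2 or 3 creatinine increase:** hold the infusion, give methylprednisolone 0.5-1 mg/kg/day, and "Monitor creatinine every 2-3 days". If the elevation lasts more than 7 days or worsens, the follow-up instruction is "Treat as Grade 4".
- **Grade 4 creatinine increase:** stop protocol therapy, give methylprednisolone 1-2 mg/kg/day by the IV route, consult a nephrologist, and "Monitor creatinine weekly".

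Two other laboratory rules in the protocol can be set beside this.

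- **Liver tests (Section 6.5.1, also suggested guidance):** "Increase LFT monitoring to every 3 days" at Grade 2, then "Increase LFT monitoring to every 1-2 days" at Grade 3 or 4.
- **Blood counts (Section 8.1 table, footnotes 2 and 3):** routine counts are weekly. In Cycle 1, "If patients have Grade 4 neutropenia then CBCs should be checked at least every other day until recovery to Grade 3". In later cycles, "If patients develop Grade 4 neutropenia then CBCs should be checked every 3 to 4 days until recovery to Grade 3".

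Routine creatinine in the Section 8.1 table is weekly in Cycle 1 and then once before each later cycle.

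**The concern.** Monitoring of an organ toxicity should be at least as close at the worse grade. Here it loosens. The escalation instruction brings in a second group as well: patients with a Grade 2 or 3 elevation that has not responded within 7 days, or has worsened, are also sent to the weekly row.

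The stake is patient safety. A site that follows the row as printed could go up to 7 days without a creatinine value in a child or young adult whose kidney injury is severe or has failed first-line steroids, and whose steroid dose has just been raised. Those are the days in which the treating team needs to know whether the higher dose is working.

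The event is uncommon but foreseeable. Acute kidney injury is in the adverse event lists for both agents (Sections 9.1.9 and 9.2.8). The one DLT reported at Part C dose level 2 was a creatinine elevation (Section 2.5). Part E gives ipilimumab at 3 mg/kg, against 1 mg/kg in Part C, with nivolumab lowered to 1 mg/kg from the 3 mg/kg of that dose level.

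**Working it through.** The plan states no summary figure to reproduce. The check converts each stated interval to a rate, checks per week = 7 / interval in days, and compares rates within each organ system.

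| Test | Source | Lower severity | Higher severity | Change in rate |
|---|---|---|---|---|
| Creatinine | 6.13.1 | Grade 2-3: 7/3 = 2.33 to 7/2 = 3.5 | Grade 4: 7/7 = 1 | down 57-71% |
| Liver tests | 6.5.1 | Grade 2: 7/3 = 2.33 | Grade 3-4: 7/2 = 3.5 to 7/1 = 7 | up 1.5 to 3 times |
| Blood counts, Cycle 1 | 8.1, footnote 2 | routine: 1 | Grade 4 neutropenia: at least 7/2 = 3.5 | up at least 3.5 times |
| Blood counts, later cycles | 8.1, footnote 3 | routine: 1 | Grade 4 neutropenia: 7/4 = 1.75 to 7/3 = 2.33 | up 1.75 to 2.33 times |

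**Creatinine.** 1 - 1/2.33 = 57% and 1 - 1/3.5 = 71%. The gap between values becomes 7/3 = 2.33 to 7/2 = 3.5 times as long.

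**Liver tests.** 3.5/2.33 = 1.5 and 7/2.33 = 3.

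**Limits of the comparison.** The grade boundaries differ: the renal step is from Grade 2-3 to Grade 4, the hepatic step from Grade 2 to Grade 3-4, and the blood-count rule is a single trigger at Grade 4 neutropenia. The comparison is one of direction, not of like-for-like size. On direction, the renal row is the only one that falls.

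**Against the routine schedule.** Weekly equals the routine creatinine rate of Cycle 1. After Cycle 1 routine creatinine is once per 21- or 28-day cycle, so weekly is 21/7 = 3 to 28/7 = 4 times that rate. The Grade 4 row is therefore not below routine monitoring; it is below the protocol's own rate for milder kidney injury. The after-Cycle-1 ratio is also of limited use, because a Grade 4 patient stops therapy and has no next cycle.

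**Whether another section sets a closer interval.** None does.

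- Section 10.1 keeps the Section 8.1 observations going for patients removed in Cycle 1 (Parts A and B) or Cycles 1-2 (Parts C, D and E), which for creatinine means weekly at most. For later removals it asks only for whatever observations adequate care requires.
- The post-therapy table in Section 8.1.1 lists no creatinine.
- Section 7.3 asks in general terms for close monitoring of possible immune-mediated events and gives no interval.

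Weekly is thus the only creatinine interval the protocol gives specifically for Grade 4.

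**The case against.** The strongest reply is that no clinician would read the weekly line alone. The table is guidance. The same row stops therapy, moves steroids to the IV route at a higher dose and calls in a nephrologist, all of which imply more contact than one blood draw a week. The instruction to treat a persistent elevation as Grade 4 can be read as raising treatment without ending the 2-3 day checks already under way. Sections 7.3 and 10.1 contain general duties of close monitoring and adequate care. The weekly interval may be a faithful copy of the brochure, which is not available here. Parts A to D are complete, Part E enrols at most 23 patients, and the only creatinine DLT reported so far was one Grade 2 event among 12 evaluable patients at Part C dose level 2.

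Much of this is fair. It makes actual harm less likely, keeps the number of exposed patients small, and means the percentages above describe testing frequency, not patient risk. The origin of the weekly figure cannot be settled from the documents.

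None of it defends the interval. Relying on the nephrologist to override the line accepts that the line should not be followed. Advisory tables matter most for uncommon events, where a site has little experience of its own. The general duties of care supply no number, whereas Section 6.13.1 does, and its number goes the wrong way.

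**Conclusion.** The point holds. As printed, the renal algorithm cuts creatinine checks from 2.3-3.5 per week to 1 when kidney injury reaches Grade 4 or fails to settle at Grade 2-3, and lengthens the gap between values from 2-3 days to 7. This is a patient-safety defect in a stated schedule, and it should be corrected. It does not touch any sample size, error rate or stopping rule in Section 11.

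The conclusion assumes that a site may follow the table literally and that the escalation instruction carries the whole Grade 4 row with it, monitoring included. If sites keep the 2-3 day checks for escalated patients, the defect is confined to those with Grade 4 creatinine. It does not depend on whether the weekly interval began as a transcription slip or comes from the brochure.

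**What to change.** Change the monitoring line in the Grade 4 row of Section 6.13.1 to: check creatinine at least every 2-3 days, or more often as nephrology directs, until it improves. This makes the protocol's own Grade 2-3 rate the floor and leaves closer monitoring to the specialist. Before issuing it, compare the line with the renal algorithm in the Investigator's Brochure to confirm the exact interval. If the brochure is tighter, use its interval.

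The cost is one line in an amendment or site memo and, at the slower rate, 2.33 - 1 = about 1.3 extra blood draws per week (3.5 - 1 = 2.5 at the faster rate) in a rare patient while creatinine remains elevated. No analysis or sample size changes.

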**6.14 Dose Modifications for Nivolumab + Ipilimumab Cardiac Toxicities**

Cardiac Toxicities *	Nivolumab + Ipilimumab Cardiac Toxicities
≤ Grade 1	Hold dose pending evaluation and observation.** Evaluate for signs and symptoms of CHF, ischemia, arrhythmia or myositis. Obtain history EKG, CK (for concomitant myositis), CK-MB. Repeat troponin, CK and EKG 2-3 days. If troponin and labs normalize may resume therapy. If labs worsen or symptoms develop then treat as below. Hold pending evaluation.
Grade ≥ 2 with suspected myocarditis	Hold dose.** Admit to hospital. Cardiology consult. Rule out MI and other causes of cardiac disease. Cardiac Monitoring. Cardiac Echo. Consider cardiac MRI and cardiac biopsy. Initiate high dose methylprednisolone. If no improvement within 24 hours, add either infliximab, ATG or tacrolimus. Resume therapy if there is a return to baseline and myocarditis is excluded or considered unlikely.
Grade ≥ 2 with confirmed myocarditis	Off protocol therapy. Admit to CCU (consider transfer to nearest Cardiac Transplant Unit). Treat as above. Consider high dose methylprednisolone Add antithymocyte globulin (ATG) or tacrolimus if no improvement. Off treatment.

*Including CHF, LV systolic dysfunction, Myocarditis, CPK, and troponin  **Patients with evidence of myositis without myocarditis may be treated according as "other event"
 
Note: The optimal treatment regimen for immune mediated myocarditis has not been established. Since this toxicity has caused patient deaths, an aggressive approach is recommended.
	

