#### 5.4.1 Non-Hematological DLT:

- Any Grade 3 or Grade 4 non-hematological toxicity attributable to protocol therapy with the specific exclusion of:
  - a. Grade 3 ALT that returns to levels that meet initial eligibility criteria or baseline within 7 days and does not require systemic immunosuppression. **Note:** For the purposes of this study the ULN for ALT is defined as 45 U/L. Adverse event grades will be based on increases above the upper limit of normal, regardless of the subject's baseline. See [Appendix IX](#) for toxicity grading table.
  - b. Grade 3 liver enzyme elevation, including AST/SGT that returns to baseline within 7 days and does not require systemic immunosuppression.
  - c. Grade 3 or 4 serum electrolyte or mineral abnormalities responsive to supplementation.
  - d. Grade 3 or 4 amylase or lipase abnormalities that are not associated with diabetes mellitus (DM), associated liver or gall bladder inflammation clinical manifestations of pancreatitis and which decrease to  $\leq$  Grade 2 within 7 days.
  - e. Grade 3 rash/oral lesions that resolves to Grade  $\leq$  1 within 7 days
  - f. Fever greater than 40°C of  $\leq$  24 hr duration
  - g. Grade 3 fatigue that resolves to Grade  $\leq$  2 within 7 days
  - h. Grade 3 creatinine increased that resolves to Grade  $\leq$  1 or baseline within 7 days
  - i. Grade 3 pleural effusion that resolves per [Section 6.8](#)
- Grade 2 fever that does not resolve to Grade  $\leq$  1 within 7 days
- Grade 2 uveitis, eye pain, or blurred vision that does not respond to topical therapy and does not improve to Grade 1 prior to next scheduled dose
- Grade 2 non-hematological toxicity requiring systemic immunosuppressive therapy, including but not limited to, autoimmunity of the lung, heart, kidney, bowel, CNS, pituitary or eye, with the specific exclusion of:
  - a. Grade 2 pleural effusion that resolves per [Section 6.8](#)
  - b. Drugs will be held for grade 2 cardiac dysfunction pending evaluation.
- Grade 2 endocrine toxicity requiring hormone replacement, with the exception of Grade 2 hypothyroidism, thyroiditis and thyroid dysfunction adequately managed with thyroid hormone replacement (see [Section 6.11](#))
- Grade 2 adrenal insufficiency
- Parts A and B: Grade 2 colitis or Grade 2 diarrhea attributable to protocol therapy that persists for  $>$  7 days will be considered a DLT.

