- Parts C, D, and E: Grade 2 colitis or Grade 2 diarrhea attributable to protocol therapy of any duration will be considered a DLT.
- Any non-hematological toxicity requiring  $>$  7 days delay in therapy will be considered a DLT

- Note: Allergic reactions that necessitate discontinuation of study drug will not be considered a dose-limiting toxicity.

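### Section 6.14 lets therapy resume after a Grade 3-4 cardiac event without asking whether it is a DLT, although Section 6.2 requires removal if it is

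*Combined protocol and SAP*

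**What the plan says.** Section 6.14 has three rows: Grade 1 or lower, Grade 2 or higher with suspected myocarditis, and Grade 2 or higher with confirmed myocarditis. The confirmed row takes the patient off therapy. The suspected row holds the dose and orders admission and a cardiac work-up. It also says "Initiate high dose methylprednisolone", with further immunosuppression if there is no improvement in 24 hours. It then closes with "Resume therapy if there is a return to baseline and myocarditis is excluded or considered unlikely". A footnote sets the scope of the table: "Including CHF, LV systolic dysfunction, Myocarditis, CPK, and troponin".

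The rules that govern DLTs sit elsewhere:

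- Section 5.4 counts events judged possibly, probably or definitely attributable, and applies one definition to all parts.
- Section 5.4.1 includes "Any Grade 3 or Grade 4 non-hematological toxicity attributable to protocol therapy with the specific exclusion of", followed by items a to i. None of these is cardiac.
- Section 6.2 removes patients with a non-hematological DLT from protocol therapy, apart from exceptions in Sections 6.3 to 6.12.
- Section 5.2 lets a further cycle start only if no DLT has occurred. Its two listed exceptions concern pancreatic function and pleural effusion.

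**The concern.** A site managing a cardiac event will open the cardiac table. For one class of event, that table gives the opposite instruction from the rules that decide whether the patient may be dosed again. The event could be severe enough to have needed admission and high-dose steroids, in a child or young adult on the higher ipilimumab dose. Section 6.14 itself notes that immune-mediated myocarditis has caused deaths and advises an aggressive approach. The row does not even require myocarditis to be ruled out; judging it unlikely is enough.

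What is at stake is re-dosing against protocol. The toxicity count is not at stake for Grade 3-4 events, because their DLT status is fixed by Section 5.4.1 and nothing in Section 6.14 alters it.

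**Working it through.** No arithmetic applies; this is a check of one rule against others. Take a Part E patient with Grade 3 left ventricular systolic dysfunction and suspected myocarditis. It resolves to baseline, myocarditis is thought unlikely, and attribution to therapy is possible.

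| Rule | Test | Result |
|---|---|---|
| 6.14, suspected row | At baseline, myocarditis unlikely | Resume |
| 5.4 | Attribution at least possible | Counts towards DLT |
| 5.4.1 | Grade 3, non-hematological, not in items a to i | DLT |
| 6.2 | DLT; 6.14 lies outside 6.3 to 6.12 | Remove from therapy |
| 5.2 | DLT has occurred; neither listed exception applies | No further cycle |

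The first line and the last two cannot all be followed. Removal comes from 6.2; 5.2 separately blocks the start of another cycle.

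Varying the case shows where the conflict ends:

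- **Attribution unrelated or unlikely.** The event is not a DLT under 5.4, and 6.14 stands without conflict.
- **Myocarditis confirmed.** 6.14 itself stops therapy, so there is no conflict.
- **No suspicion of myocarditis.** The resumption row does not apply, and 5.4.1 and 6.2 govern.
- **Grade 2.** The text is unclear rather than contradictory. Section 5.4.1 counts "Grade 2 non-hematological toxicity requiring systemic immunosuppressive therapy, including but not limited to, autoimmunity of the lung, heart, kidney, bowel" and other sites as a DLT. Its exclusion list then contains "Drugs will be held for grade 2 cardiac dysfunction pending evaluation", which is a hold instruction and does not settle DLT status. An attributable Grade 2 event is a DLT in any case if it causes more than "7 days delay in therapy will be considered a DLT".

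The conflict is therefore confined to Grade 3-4 events that enter the suspected-myocarditis row, return to baseline, have myocarditis excluded or judged unlikely, and remain at least possibly attributable.

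Nothing in 6.14 subordinates it to the DLT rule. Section 6.13 (renal), which also lies outside the 6.3 to 6.12 range, expressly sends DLTs back to 6.2. Sections 6.5 and 6.11 point to 5.4.1 in their tables.

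**The case against.** **Other text links cardiac events to the DLT rule.** Footnote 13 of the Section 8.1 schedule sends sites to 5.4.1 for on-study cardiac problems, together with a section numbered 6.1.4, evidently meant as 6.14. Section 10.1(c) cites 5.4 alongside 6.0. A careful reader could conclude that 5.4.1 prevails. That is fair, but neither place says so, and the row remains unqualified.

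**Several safeguards stand between the table and a dose.** Suspected DLTs go to the Study Chair within 24 hours (5.3), and dosage modifications must be notified (6.0). In Part E the study committee reviews attributed Grade 3 to 5 toxicity weekly (11.7.1), and a weekly leadership call reviews the chair's DLT evaluations (14.5). Combination doses are 21 days apart. These make an actual wrongful re-dosing much less likely. They do not correct the instruction.

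**If it is not myocarditis, it is not attributable.** This does not follow. The table also covers heart failure, ventricular dysfunction and enzyme rises, and possible attribution is enough for a DLT.

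**The 6.3 to 6.12 range may simply be out of date.** It may be. In that case 6.2 and 5.2 need correcting instead, and the present text still conflicts.

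A reader might also infer that 6.14 is the only section allowing treatment after a Grade 4 event. The documents do not support this. A footnote in 6.10.1 exempts decreased tendon reflex of any grade from dose modification. The Grade 3/4 rash row of 6.4.1 says to hold, although the 6.4 table itself stops therapy at Grade 4. The absence of a DLT pointer is not unique to 6.14 either; what matters is that 6.14 lies outside the exceptions 6.2 allows.

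**Conclusion.** The suspected-myocarditis row is wrong as written for Grade 3-4 cardiac events at least possibly attributable to therapy. It permits resumption where 5.4.1, 6.2 and 5.2 together end treatment. It should be corrected because the subject is safety and the correction is nearly free.

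The practical size is small. Sections 5.1.1 to 5.1.4 mark Parts A to D as completed, and Part E enrolls at most 23 patients. Several conditions must coincide, and the safeguards above may intercept a case. The documents give no rate for such events, and none is assumed here.

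Two wider conclusions are not supported. One is that the Grade 2 rules contradict each other; they are only unclear. The other is that children will in practice be re-dosed against protocol; that would require the reporting and review steps to fail as well.

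The verdict rests on reading 6.2 and 5.2 as governing, because they state the general consequence of a DLT and name their own exceptions.

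**What to change.** In the suspected-myocarditis row of Section 6.14, keep the two existing conditions for resuming and add a third: *and the event is not a DLT under Section 5.4.1; if it is a DLT, off protocol therapy per Section 6.2.* This follows the governing rules as they now stand and needs no change to 6.2 or 5.2.

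If the sponsor did intend to allow rechallenge after such a DLT, the repair goes the other way: extend the exceptions in both 6.2 and 5.2 to name 6.14. The sponsor should confirm which it means.

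Two clarifications are optional. Item b under the Grade 2 bullet of 5.4.1 could say whether steroid-treated Grade 2 cardiac dysfunction is a DLT. The second footnote of 6.14, which begins "Patients with evidence of myositis without myocarditis may be treated according as", sends the reader to a category with no rule of its own in Section 6; it could point to 5.4.1 and 6.2. Its overlap with the myopathy stop rule in 6.10 would still need a decision.

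The main change costs one clause in one row, carried in an amendment. It adds no patients, visits or tests.
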